10. ADMINISTRATIVE, ETHICAL, REGULATORY CONSIDERATIONS

10.1. Informed Consent

Informed consent will be obtained in accordance with the Declaration of Helsinki, ICH GCP, US Code of Federal Regulations for Protection of Human Subjects (21 CFR 50.25[a,b], CFR 50.27, and CFR Part 56, Subpart A), the Health Insurance Portability and Accountability Act (HIPAA, if applicable), and local regulations.

The Investigator will prepare the informed consent form and HIPAA authorization and provide the documents to submit to the IRB/IEC. The consent form generated by the Investigator must be approved by the IRB/IEC. The written consent document will embody the elements of informed consent as described in the International Conference on Harmonisation and will also comply with local regulations. The Investigator will send an IRB/IEC-approved copy of the Informed Consent Form for the study file.

A properly executed, written, informed consent will be obtained from each subject prior to entering the subject into the trial. Information should be given in both oral and written form and subjects must be given ample opportunity to inquire about details of the study. A copy of the signed consent form will be given to the subject and the original will be maintained with the subject's records.

Any documents that the institutional review board may need to fulfill its responsibilities (such as protocol, protocol amendments, consent forms, information concerning patient recruitment, payment or compensation procedures, or other pertinent information) will be submitted to the institutional review board. The institutional review board's written unconditional approval of the study protocol and the informed consent form will be in the possession of the Investigator before the study is initiated. This approval must refer to the study by exact protocol title and number and should identify the documents reviewed and the date of review.

Protocol and/or informed consent modifications or changes may not be initiated without prior written institutional review board approval except when necessary to eliminate immediate hazards to the patients or when the change(s) involves only logistical or administrative aspects of the study. Such modifications will be submitted to the institutional review board and written verification that the modification was submitted and subsequently approved should be obtained. The institutional review board must be informed of revisions to other documents originally submitted for review; serious and/or unexpected adverse experiences occurring during the study in accordance with the standard operating procedures and policies of the institutional review board; new information that may affect adversely the safety of the patients of the conduct of the study; an annual update and/or request for re-approval; and when the study has been completed.

11. APPENDICES

11.1. Appendix A: The Migraine Disability Assessment Test (MIDAS)

Over the past _____, please answer the following questions about ALL headaches you have had.

_____1. On how many days in the last ______ did you miss work or school because of your headache?

2. How many days in the last _____ was your productivity in work or school reduced by half or more because of your headaches? (Exclude days that were counted in question #1 where you missed work or school)

3. How many days in the last did you not do household work (such as housework, repairs, maintenance, shopping, caring for yourself, children, relatives) because of your headaches?

4. How many days in the last _____ was your productivity in household work reduced by half or more because of your headaches? (Exclude days that were counted in question #1 where you did not do any household work)

_____ 5. How many days in the last ______ did you miss family, social, or leisure activities because of your headaches?

MIDAS Grade	Definition	MIDAS Score
Ι	Little of No Disability	0-5
II	Mid Disability	6-10
III	Moderate Disability	11-20
IV	Severe Disability	21+

Add the total number of days from questions 1-5:

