4.2. Secondary Objectives

Efficacy is a secondary outcome that will be examined. The endpoints for evaluation include difference in MIDAS, 4-point verbal pain scale, and 11-point numeric pain scale scores prior to drug administration and 1 week, 6 weeks, and 3 months after drug administration.

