6.4. Screening

Upon enrollment, the neurological provider will be asked to verify past medical history (i.e., tobacco use, obesity status, past traumatic brain injury, diabetes mellitus, hypertension, hyperlipidemia) and current medications during the clinical encounter. Patients would undergo a pre-treatment serum metabolic blood panel to document baseline serum glucose levels, which is a routine biomarker to assess prior to administering glucocorticoid medications. Specific for research purposes only, patients would also be asked to score baseline MIDAS, 4-point verbal rating scale, and 11-point numeric pain scores (Appendix G). Patients will be instructed to keep a Study Diary, and will be instructed to record migraine episodes and any adverse events with date of onset, duration, and description for four weeks before and three months after treatment.

Patients with baseline serum glucose of above 400 mg/dL will fail screening procedures and not be included within the study due to elevated risk of acute exacerbation of steroid hyperglycemia during methylprednisolone administration.

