7. STUDY TREATMENT, PROCEDURES, AND GUIDELINES

7.1. Study Intervention

After baseline screening assessment, patients will be scheduled within one month for investigational drug administration. Xylocaine®-MPF will be prepared for administration of 40 mg of active lidocaine hydrochloride per dose as described in Section 3.1.4. A total of two doses (40 mg lidocaine hydrochloride per dose; 80 mg total) of lidocaine hydrochloride will be prepared for the injection of each dose into each middle meningeal artery (left and right). SOLU-MEDROL® will be prepared for administration of 20 mg of active methylprednisolone sodium succinate as described in Section 3.1.4. A total of two doses (20 mg methylprednisolone sodium succinate per dose; 40 mg total) of methylprednisolone sodium succinate will be prepared for the injection of each dose into each middle meningeal artery (left and right). No placebo agents will be used during the study. Agents will not be blinded. Agents will be prepared and stored per instructions contained within Section 16 (HOW SUPPLIED/STORAGE AND HANDLING) of the Prescribing Information and manufactures' guidelines contained within the packaging insert.

The treatment will be administered in the Acute Stroke and NeuroInterventional Suite at Cooper University Health Care. The care team will include an experienced neurointerventional physician with extensive experience in proper catheter placement and technical specifications necessary for the procedure below, certified and licensed angiography technicians, a dedicated anesthesiology care team, pharmacy team, and nursing team comprised of neurocritical care certified nurses (including post-procedural recovery and observation). Within the immediate treatment area, availability to resuscitative equipment and continuous vital sign monitoring, including rapid cycling continuous blood pressure monitoring (with measurements at least every 5 minutes), continuous pulse oximetry, respiratory rate, continuous heart rate monitor, and electrocardiographic monitoring, will be ensured. For safety, patients may be sedated using institutional monitored anesthesia care (MAC) protocol under the care of a licensed anesthesiologist, and thus will not require intubation. Patients will be monitored continuously throughout the procedure and for four hours post-operatively in a dedicated post-angiography care unit.

The following steps will be performed interprocedurally:

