7.2.1. Visit 1 (Screening)

- 1. Review the study with the subject and obtain written informed consent and HIPAA authorization.
- 2. Assign the subject a unique screening number.
- 3. Record demographics data.
- 4. Record medical history, including history of tobacco use, obesity status, past traumatic brain injury, diabetes mellitus, hypertension, hyperlipidemia, migraines), diagnosis date, and prior preventative medications trialed for migraine treatment.
- 5. Record current, concomitant medications.
- 6. Perform a complete neurological physical exam, including visual field assessment, fundoscopic exam, cranial nerve exam, peripheral motor and sensory fields, and reflexes.
- 7. Perform and record vital signs, including blood pressure monitoring.
- 8. Perform clinical laboratory tests (i.e., complete metabolic blood panel and pregnancy test as applicable).
- 9. Administer migraine-related symptom scores (i.e., MIDAS, 4-point Verbal Rating Scale, 11-point Numeric Pain Rating Scale).
- 10. Initiate Subject Diary, including instructions to record migraine episodes and any adverse events with date of onset, duration, and description.
- 11. Schedule subject for Visit 2 (study drug administration).

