9. STATISTICAL METHODS AND CONSIDERATIONS

9.1. Analysis Plan

An intention to treat analysis will be performed. Prevalence of any adverse event, treatment-related adverse events, and serious and/or fatal adverse events will be calculated. Secondary analyses assessing pairwise differences in pre- and post-interventional changes in symptom scores will also be performed to identify trends and as the basis for future power analyses. Categorical variable data will be summarized as frequencies with Agresti-Coull intervals as applicable. Quantitative variable data will be summarized as medians with interquartile ranges. Spearman's rank correlation coefficient, two-sided Student's t-test, chi-square tests, and nonparametric equivalences may be conducted at 0.05 significance level.

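### The MIDAS form states no recall window and its question 4 cites the wrong question, so the plan does not define the pre/post MIDAS differences it will report

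*Combined protocol and SAP*

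**What the plan says.** Appendix A (section 11.1) prints the MIDAS form with a line to fill in where the recall period belongs: "Over the past _____, please answer the following questions about ALL headaches you have had". The blank recurs in the questions. The score is a plain count: "Add the total number of days from questions 1-5". Fixed grade cut-offs follow (0-5, 6-10, 11-20, 21+).

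Question 1 asks about missed work or school, and question 3 about household work not done. Question 4, on reduced household productivity, carries the instruction "Exclude days that were counted in question #1 where you did not do any household work".

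Section 4.2 makes the MIDAS difference a secondary efficacy endpoint, comparing scores "prior to drug administration and 1 week, 6 weeks, and 3 months after drug administration". Section 9.1 analyses the paired changes "to identify trends and as the basis for future power analyses".

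On baseline, section 6.4 says that at screening "patients would also be asked to score baseline MIDAS". Section 7.1 continues: "After baseline screening assessment, patients will be scheduled within one month for investigational drug administration". Table 1 also lists MIDAS at Visit 2, and section 7.2.2 places it after drug administration.

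**The concern.** A sum of days has no meaning without the number of days recalled. Sections 4.2, 5.1, 6.4, 7.2 and 9.1 neither give that number, nor require it to be equal at all visits, nor convert scores to a common scale. The diary period in section 6.4 is the only look-back in the plan, and it is not tied to MIDAS.

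Two things can go wrong, depending on how staff fill the blank. A long common window makes an early post-dose score partly a pre-dose score, which hides a real effect. A window that is shorter after dosing than at baseline makes the score fall when nothing has changed. With up to 10 patients and no control arm, the data would not reveal either error, and the estimate is meant to feed the sample size of a later trial.

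The question 4 error is independent of the window. It affects the score at every visit.

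**Working it through.** **Inputs.** Visit days from sections 7.2.3 to 7.2.5: t = 7, 42 and 84, each ± 2 days. Visit 1 is about 28 days before dosing (section 7.2.2). The documents give no window W, so W = 7, 28 and 90 days are assumptions that show the range. The plan states no figure to reproduce.

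**Common window: share of recalled days before dosing** = max(0, W − t)/W.

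| W | Week 1 (t = 7) | Week 6 (t = 42) | Week 12 (t = 84) |
|---|---|---|---|
| 7 | 0% | 0% | 0% |
| 28 | 21/28 = 75% | 0% | 0% |
| 90 | 83/90 = 92.2% | 48/90 = 53.3% | 6/90 = 6.7% |

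Across the ± 2 days, the week-1 share runs from 67.9% (19/28) to 82.1% (23/28) for 28 days and from 90.0% to 94.4% for 90 days. A 7-day window includes 2 pre-dose days (2/7 = 28.6%) if Visit 3 falls on day 5. The threshold is therefore the actual visit day, 5 to 9. Any window over 9 days takes in pre-dose days for every patient seen within the allowed range.

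**What a true 50% fall would look like.** Assume a constant daily rate before dosing and an immediate, lasting halving after it. The apparent fall is 50% × (1 − share).

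| W | Week 1 | Week 6 | Week 12 |
|---|---|---|---|
| 7 | 50% | 50% | 50% |
| 28 | 12.5% | 50% | 50% |
| 90 | 3.9% | 23.3% | 46.7% |

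With 90 days, the Visit 1 window covers days −118 to −28 and the week-1 window days −83 to 7. The two scores share 55 recalled days. At week 6 they share 20 (days −48 to −28), and at week 12 none.

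**Unequal windows, no effect.** Take a 90-day baseline against recall since treatment. The apparent change is t/90 − 1: −92.2%, −53.3% and −6.7%. Grades move too. An unchanged patient at an assumed 0.5 points per day scores 3.5 over 7 days (grade I), 14 over 28 days (grade III) and 42 over 84 days (grade IV).

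**Question 4.** Suppose there are 5 question 3 days and the correct question 4 answer is 5.
- Reading the instruction as question 1 days on which no household work was done, question 3 days that are not question 1 days are not excluded. The answer can rise to 5 + 5 = 10.
- Reading it as all question 1 days, valid question 4 days that were also missed work or school days are dropped. The answer can fall to 5 − 5 = 0.

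The error can therefore run in either direction.

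**The case against.** **The blank is meant to be filled in at each visit.** That is plausible for a fill-in form, but no rule says what to enter, and visit-specific entries without rescaling give the spurious changes shown above.

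**The missing rule may be elsewhere.** Sections 5.1 and 6.4 cite an Appendix G for these scales, which is not in the available text. That limit stands. Against it, the table of contents lists only Appendices A to C, and Table 1 sends the reader to Appendix A for MIDAS. The supportable claim is that the available text does not specify the window.

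**The sizes are hypothetical.** This is fair. A reader might infer that the trial's MIDAS result will be diluted or inflated by these amounts. The documents do not support that, because they do not say which window will be used.

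**The Visit 2 step order looks like a conflict.** A reader might infer that a post-dose score is being taken as baseline. Section 5.1 plans symptom scores at the evaluation straight after the procedure, so a MIDAS listed after dosing fits that plan, while sections 6.4 and 7.1 tie baseline to screening. What remains is that sections 4.2 and 9.1 do not name the baseline visit.

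**The question 4 intent is readable, and the same wording is used at every visit.** Some of the error may cancel in differences. Nothing ensures that patients read it consistently.

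**Conclusion.** The point holds and should be fixed before MIDAS data are collected, since recall over the right period cannot be reliably rebuilt afterwards. As written, the week-1 MIDAS difference is uninterpretable under any common window over 9 days, and under a 90-day window the week-6 difference is roughly halved as well. These sizes rest on assumed windows, a constant daily rate and an immediate effect.

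Two stronger statements go too far. The first is that every window over 7 days contaminates week 1: an 8- or 9-day window is clean for a day-9 visit, and a 7-day window is not clean for a day-5 visit. The second is that question 4 only inflates the score.

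The scope is one of three efficacy scales. The Protocol Summary lists MIDAS among the primary efficacy variables, but section 4.2 places efficacy as secondary. The adverse-event outcome and the two pain scales do not depend on the window.

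**What to change.** 1. In question 4, change the reference from question 1 to question 3.
2. Print the recall window on the form so that no post-dose window reaches back before dosing. There are two ways:
   - One fixed window at baseline and follow-up, with no MIDAS difference at a visit earlier than that window. With 4 weeks, weeks 6 and 12 are clean (earliest visit day 40) and week 1 relies on the two pain scales.
   - Visit-specific windows (since dosing at week 1), with every score, including baseline, expressed per day or per 28 days before differencing. The unchanged patient above then scores 3.5 × 28/7 = 14 at week 1 and 14 at baseline.
3. State in sections 4.2 and 9.1 that the Visit 1 MIDAS is the baseline, and that the Visit 2 score belongs to the immediate post-procedure assessment and is not used as baseline.

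The cost is a form correction and a few sentences. The first option gives up the week-1 MIDAS difference, a stated endpoint. The second keeps it on few days: one day in one question moves the rescaled week-1 score by 28/7 = 4 points (5.6 at day 5, 3.1 at day 9). The printed grade cut-offs do not apply to short or rescaled windows, though the grade is not an endpoint. The diary cannot check a Visit 1 recall, because Visit 1 is where staff "Initiate Subject Diary, including instructions to record migraine episodes".

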11.2. Appendix B: 4-Point Verbal Pain Scale

Score	Pain Descriptor	Severity of Pain
0	None	No pain
1	Mild	Pain reported in response to questioning only, without any behavioral signs
2	Moderate	Pain reported in response to questioning and accompanied by behavioral signs, or pain reported spontaneously without questioning
3	Severe	Strong verbal response accompanied by facial grimacing, withdrawal of the hand, or tears

Provider, please ask: "How would you describe your pain?"

Grade is determined based on patient descriptor and provider interpretation based on criteria in "Severity of Pain" column

11.3. Appendix C: 11-Point Numeric Pain Scale

Provider, please ask: "On a scale of 0-10, with 10 being the worst pain imaginable, how would you rate your headache-related pain?"

Score	Pain
0	No Pain
1	
2	
3	
4	
5	
6	
7	
8	
9	
10	Worst Pain Imaginable

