5. STUDY DESIGN

5.1. General Approach for Evaluation of Treatment

This study will be a non-randomized, open-label phase 1 clinical trial. Participants above the age of 18 years who have an established diagnosis of intractable migraine (defined as failure of four other pharmacologic agents) and are active patients at our institution (i.e., have an appointment with a neurologic care provider during the enrollment period) will be offered enrollment. Either intolerance or side effects requiring early discontinuation or adequate trial at therapeutic dose without relief constitutes failure of therapy.

A neurological provider will perform a baseline assessment of enrolled patient's medical history and symptom scale scores, including MIDAS, 4-point verbal pain scale, and 11-point

numeric pain scales (Appendix G). An experienced neurointerventional co-investigator will inject 20 mg methylprednisolone and 40 mg lidocaine into the middle meningeal artery bilaterally. Each patient will receive a total of two doses of the 40mg lidocaine/20mg methylprednisolone co-administration of drugs (i.e., one dose administered within the left middle meningeal artery, and the other dose in the right middle meningeal artery). Immediate post-operative clinical evaluation, and evaluation at subsequent follow-up appointments with a neurological provider will involve assessment of neurological functional status, symptom scores, and occurrence of any associated adverse event at 1 week, 6 weeks, and 3 months. To evaluate the primary safety outcome, data will be analyzed to yield the prevalence of any adverse event, treatment-related adverse events, and serious and/or fatal adverse events. Data comparing pairwise differences in pre- and post-drug changes in symptom scores at 1-week, 6-week, and 3-month follow-up clinical encounters will be analyzed to assess secondary efficacy outcome.

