7.2.2. Visit 2 (Administration)

(Week 0 – Approximately 4 weeks after Visit 1).

- 1. Record any changes to concomitant medications.
- 2. Perform a complete neurological physical exam, including visual field assessment, fundoscopic exam, cranial nerve exam, peripheral motor and sensory fields, and reflexes.
- 3. Perform and record vital signs, including blood pressure monitoring.
- 4. Administer study drug (lidocaine hydrochloride and methylprednisolone serially).
- 5. Perform clinical laboratory tests (i.e., complete metabolic blood panel) following study drug administration.
- 6. Administer migraine-related symptom scores (i.e., MIDAS, 4-point Verbal Rating Scale, 11-point Numeric Pain Rating Scale).
- 7. Review Subject Diary, including details of any migraine episodes.
- 8. Schedule subject for Visit 3.

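### The pain-scale baseline is one screening score about 4 weeks before dosing, and neither pain item has a recall window, so attack timing may cost precision in two secondary scores

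*Combined protocol and SAP*

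**What the plan says.** Section 4.2 defines efficacy as the difference between scores before drug and scores at 1 week, 6 weeks and 3 months, on MIDAS, the verbal scale and the numeric scale. Section 9.1 uses these differences to look for trends and to inform later power calculations.

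- **Baseline.** Section 5.1 calls for a baseline assessment of symptom scores in enrolled patients, and section 6.4 places it at screening: "patients would also be asked to score baseline MIDAS, 4-point verbal rating scale, and 11-point numeric pain scores". Section 7.2.1 collects the scores at step 9. Dosing follows about 4 weeks later (section 7.2.2).
- **Visit 2.** Table 1 marks all three scales at Visit 2 but gives no order within the visit. In section 7.2.2, step 4 is "Administer study drug (lidocaine hydrochloride and methylprednisolone serially", step 5 is "Perform clinical laboratory tests (i.e., complete metabolic blood panel) following study drug administration", and the symptom scores are step 6. Section 5.1 adds: "Immediate post-operative clinical evaluation, and evaluation at subsequent follow-up appointments with a neurological provider will involve assessment of neurological functional status, symptom scores". Section 7.1 says "patients may be sedated using institutional monitored anesthesia care (MAC) protocol".
- **Wording of the items.** The numeric item (Appendix C) is "On a scale of 0-10, with 10 being the worst pain imaginable, how would you rate your headache-related pain". It does not ask for pain now, average pain or worst pain, and it names no period. The verbal item (Appendix B) names no period either, and "Grade is determined based on patient descriptor and provider interpretation", using behaviour such as grimacing or tears.
- **Diary.** Under section 6.4 patients record migraine episodes, with onset date and duration, for four weeks before and three months after treatment. Neither 4.2 nor 9.1 turns these into an efficacy summary.

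**The concern.** The only pain score certain to precede the drug is a single reading about 4 weeks earlier. If the Visit 2 list is followed in order, that day's score comes after the drug, and possibly after sedation, so it cannot serve as a second baseline.

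Without a recall window, a patient may answer for pain at that moment, for a typical headache or for the worst recent one. The behavioural anchors push the verbal scale towards pain at the visit. If pain comes in attacks and the answer is for the moment, one reading before and one after differ partly because one visit fell in an attack and the other did not. With 10 patients and no control arm, that spread goes straight into the estimated change.

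MIDAS counts days over a period and is much less exposed, although its printed window is blank. At stake is the precision of two of the three secondary efficacy scores.

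**Working it through.** **Nothing to reproduce.** The plan gives no SD, effect size or power for the pain scales. Section 5.3 bases the sample size on phase 1 norms. What follows is illustration.

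**Inputs.** From the documents: n = 10, and one score at each visit. Assumed: patients answer for current pain; pain is 7 in an attack and 0 or 3 between attacks (gap d = 7 or 4); attack days per 28 run from 8 to 28; visits are independent.

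**Step 1: timing alone.** With f = attack days/28, the single-visit SD is d·√(f(1−f)). The SD of post minus pre is √2 times that. The 95% half-width for the mean change is 2.262 × SD/√10 (t with 9 df).

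| Attack days per 28 | SD of change, d = 7 | Half-width, d = 7 | SD of change, d = 4 | Half-width, d = 4 |
|---|---|---|---|---|
| 8 | 4.47 | 3.20 | 2.56 | 1.83 |
| 14 | 4.95 | 3.54 | 2.83 | 2.02 |
| 20 | 4.47 | 3.20 | 2.56 | 1.83 |
| 26 | 2.55 | 1.82 | 1.46 | 1.04 |
| 28 | 0 | 0 | 0 | 0 |

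If patients report typical pain, every entry is 0.

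**Step 2: share of the variance.** Add visit-to-visit noise of SD 1.5 and a true between-patient effect of SD τ (both assumed). The share is 2d²f(1−f) / (2d²f(1−f) + 2×1.5² + τ²).

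| Case | 8–20 days | 26 days | 28 days |
|---|---|---|---|
| d = 7, τ = 0 | 82–84% | 59% | 0% |
| d = 7, τ = 2 | 70–74% | 43% | 0% |
| d = 4, τ = 0 | 59–64% | 32% | 0% |
| d = 4, τ = 2 | 43–48% | 20% | 0% |

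Example, d = 4, 14 days, τ = 2: 8/(8 + 4.5 + 4) = 48%.

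A separate simulation agrees in pattern. It used mean in-attack pain of 7, pain-free visits scored 0, a true-effect SD of 1 and no mean effect. Attack state took 91–93% of the variance when half of visits fall in an attack, 62–67% at nine in ten, and 0% when all do.

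**Step 3: a second baseline.** Let all visits have single-visit variance σ² and a common correlation r. With one baseline the variance of change is 2(1−r)σ². With the mean of two it is σ²[1 + (1+r)/2 − 2r] = 1.5(1−r)σ². The ratio is 0.75 for any r, including r = 0. This applies to the visit-level part; true differences in response are untouched. At 14 days the timing-only half-width falls from 3.54 to 3.07 (d = 7) or from 2.02 to 1.75 (d = 4).

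**Step 4: a 3-day average for the numeric item.** The SD of a 3-day mean relative to one day is 1/√3 = 0.577 for independent days. For day-to-day correlation 0.7 it is √[(3 + 2(2×0.7 + 0.7²))/9] = 0.868. With two baselines at 14 days the half-width becomes 1.77 or 2.66 (d = 7), and 1.01 or 1.52 (d = 4).

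**The case against.** The strongest reply is that the plan reads coherently as it stands: screening is the baseline and Visit 2 is an acute post-procedure score. That largely stands. A reader might infer that the plan has no baseline, or that the Visit 2 score is certainly post-dose. Neither is supported. Section 6.4 names the baseline; at Visit 2 only the blood panel is expressly post-dose, and list order need not be clock order. What remains is that no pre-dose score on the dosing day is assured, and that 9.1 does not say how the Visit 2 score is to be used.

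The second reply is that the size rests on stacked assumptions. It does. The numeric item asks about headache-related pain, not pain now, so an answer for a typical headache is plausible and the timing term would then vanish. A reader might infer that most of the variance is timing; that is one branch of a range that starts at zero.

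Third, section 9.1 mainly plans medians with interquartile ranges, and the t-test is optional. The t-interval above is therefore only a yardstick, though the same visit-to-visit spread widens an interquartile range.

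Fourth, the second baseline helps modestly, and labelling the verbal scale as current pain leaves its timing noise in place. Both points stand. The label makes the score interpretable, not more precise.

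**Conclusion.** The point holds as a conditional loss of precision in two secondary efficacy scores. The textual part needs no assumed number: the baseline is about 4 weeks before dosing, no dosing-day pre-dose score is assured, and neither pain item has a recall window. The size cannot be known from the documents. If answers are for current pain of 7 in attack and 3 or 0 between, with independent visits, the timing-only half-width is about 1.8 to 3.5 points at 8 to 20 attack days per 28. It shrinks to nothing for daily pain or typical-pain answers.

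Two stronger readings should be resisted. One is bias: eligibility sets no pain score or headache frequency, and no visit is tied to attack state, so timing as described adds spread, not a shift. The other is that later power calculations are spoiled: the SD would mislead only if the later trial used a different endpoint or recall window. The primary safety objective is unaffected. This is a cheap improvement worth making, because recall wording and scoring order cannot be repaired once data are collected.

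**What to change.** 1. In section 7.2.2, state that the symptom scores are taken before study drug. In 9.1, define baseline for the two pain scales as the mean of Visit 1 and pre-dose Visit 2, and treat any post-dose Visit 2 score as acute only.
2. In Appendix C, give the numeric item one fixed recall window that cannot reach pre-dose days at Visit 3, which may fall on day 7 − 2 = 5; for example, average headache pain over the past 3 days. In Appendix B, label the verbal scale as current pain.
3. In 4.2 and 9.1, add a supplementary summary of diary migraine days per 28 days, pre-dose against post-dose windows (for example days 1–28, 29–56 and 57–84). Prorate short windows: Visit 5 may fall on day 84 − 2 = 82. This is a separate endpoint and does not sharpen the pain scores.

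Cost: a few minutes of questionnaires before dosing, data entry for a diary already kept, and a departure from the plain wording of the numeric scale.
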